2.1 KEY TERMS

BCP – beach chair position

POCD – post operative cognitive decline

CDE – cerebral desaturation event

rSO₂ – regional cerebral oxygen saturation

MAP – mean arterial pressure

BMI – body mass index

2.2 LAYMAN'S SUMMARY

Surgery to the shoulder may be performed with patients seated upright in a position known as the “Beach Chair Position (BCP).” This position has certain advantages compared to alternative surgical positions (eg side lying) in some situations. However, it has been found that surgery in the BCP can temporarily decrease the amount of oxygen in the brain as a result of the combined effects of gravity and anaesthesia. This can result in complications following surgery such as some memory loss and confusion. Rarely, more serious complications have been reported in the past including death and stroke.

Due to these reported complications the use of “cerebral oximetry” during shoulder surgery in the BCP has become more common. Before and during surgery, a monitor placed on the patients forehead measures the amount of oxygen present in the brain to help control this to an acceptable level. A number of monitors are now commercially available. Two monitors are commonly discussed in the literature; the INVOS™ 5100 and the FORE-SIGHT® machines. However, the actual relationship between the supply of oxygen to the brain

during surgery and the chance of later developing problems with memory and thinking (known as “post operative cognitive decline” – POCD) is not clear. It is also not known if one monitor is more accurate than another at predicting these complications.

Therefore, the main aim of this study is to examine the relationship between cerebral oxygen levels during shoulder surgery and the incidence of POCD (i.e. problems with memory and thinking). A second aim is to compare the INVOS™ 5100 and FORE-SIGHT® monitors ability to measure cerebral oxygen and CDE as well as the importance of other key clinical variables (e.g. blood pressure, nausea, body fat etc).

3 PURPOSE OF THE INVESTIGATION

The purpose of this investigation is to generate evidence about cerebral oxygenation during shoulder surgery and the incidence of POCD. Currently, evidence relating to POCD following surgery is conflicting and relates mostly to outcomes following cardiac surgery. There is a strong need to explore this relationship in the specific context of shoulder surgery in the BCP.

3.1 INTERVENTION GROUPS

The first study, hereby named STUDY ONE will involve a single prospective cohort. Patients who meet the selection criteria will be recruited to the study following voluntary informed consent . Cerebral

3.2 STUDY ONE

3.3 AIM OF THE STUDY

This study has three aims;

- (i) To examine the relationship between cerebral desaturation during shoulder surgery in the BCP, and the incidence of POCD.
- (ii) To determine the variation in cerebral oxygenation recorded using randomised (for superior/inferior) simultaneous application of the INVOS™ and FORE-SIGHT® oximeters, during shoulder surgery in the beach chair position.
- (iii) Assess the relationships between cerebral oxygen desaturation during shoulder surgery in the BCP and variables including mean arterial pressure, incidence of nausea/vomiting, duration of hospital stay, BMI, hypertension and adverse events.

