A number of cerebral oximeters are commercially available. Douds et al. (2014) completed a systematic review of devices commonly used in cardiac surgery and concluded that there were only a very limited number of high quality papers available. Most of these papers were based on the INVOS™ system. These authors highlighted the need for further RCTs to investigate the role of cerebral oximetry and the efficacy of devices currently available. Hessel et al., (2014) examined cerebral oxygenation in newborns using both the FORE-SIGHT® and INVOS™ monitors. They found that the FORE-SIGHT® monitor demonstrated greater repeatability and hypothesised that this may indicate a lower responsiveness to change in oxygen saturation. In contrast, Closhen et al., (2013) compared the use of the INVOS™ and FORE-SIGHT® monitors to detect oxygen saturation in the beach chair position and found no significant difference according to monitor type. The study by Bickler et al., (2013) compared the performance of several cerebral oximeter devices including the FORE-SIGHT® and INVOS™ monitors. It compares the performance of different cerebral oximetry devices using an invasive reference standard and a common sample population (health adult volunteers), simultaneous testing methodology and data analysis. It is important that the monitors are being used within their approved indication for and that care must be taken to avoid optical cross-talk between the sensors of different manufacturers. In addition, the sensors will be placed randomly on the forehead in terms of superior and inferior in the same position to avoid sequential bias. Both the FORE-SIGHT® and INVOS™ cerebral oximetry measurements have been assessed and shown to be valid surrogates for true cerebral oxygenation .

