3.6 PRIMARY HYPOTHESES

The primary research hypotheses are;

- (i) Cerebral desaturation events during surgery in the BCP will be related to POCD.
- (ii) The INVOS™ 5100 and the FORE-SIGHT® monitors will show no significant difference in their ability to measure cerebral oxygenation.
- (iii) Cerebral desaturation events experienced during shoulder surgery in the BCP are related to a drop in mean arterial blood pressure, an increased likelihood of post-operative nausea and vomiting, greater length of hospital stay, a higher BMI, hypertension and greater frequency of adverse events.

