5.5 SAMPLE SIZE

Approximately 200 participants will be recruited to the study. Based on historical patient presentation rates for this group, it is anticipated that recruitment will take approximately 24 months. This allows for 75% recruitment rate and 30% loss to follow up.

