10.1 STATISTICAL METHODS

Baseline demographic and clinical data will be examined using descriptive statistics (means, standard deviations [SDs], and percentages). Dropouts will be compared to those who complete the study. For initial data screening, descriptive statistics (means, standard deviations [SDs], and percentages) will be completed for all predictor and outcome variables. Based on the findings of de Tournay - Jette et al. (2011), we assume that 62% of patients will not experience desaturation, and that the probability of postoperative cognitive dysfunction in these patients is 29%. To observe an increased risk of cognitive dysfunction of 1.75 times in patients who experienced desaturation (i.e. to 50%) we will be required to collect postoperative data on 193 participants, assuming $\alpha=0.05$ and $\text{power}=80\%$. For the secondary outcome, which is the concordance between the INVOS™ 5100 and FORE-SIGHT® devices during shoulder surgery, the agreement between these pairs of observations will be assessed using intra-class correlation (ICC 3,1) (Portney & Watkins, 1993).

A number of statistical analyses will be used to explore the relationship between CDE and other study variables to allow for use of continuous and categorical data (e.g. linear & logistic regression). With an anticipated sample size of 200 this should provide adequate numbers for our analysis (Portney & Watkins, 1993). Prior to the use of a regression analysis, exploratory bivariate analyses (e.g. correlation, chi square, one-way ANOVA) will be conducted among all predictor variables to identify multi-collinearity. Bivariate analyses between each predictor and outcome variable will then be conducted. Significant predictor variables identified from bivariate analyses will be entered into the regression model. A process of backward elimination will then be used to identify the best model considering main effects and two-way interactions at $p \leq 0.05$. Data analysis will be conducted using SSPS version 23. Any complication rates will be reported in terms of frequency and analysed. The potential contribution of type of surgery, the length of surgery and the nature of the anaesthetic agents

used are recorded as standard practice and will be included in analyses to assess whether or not they represent confounding factors. The final multivariable model will include the main effects of interest and variables identified as potential confounders.

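### Sensor site (superior/inferior) is randomised between the oximeters, but the ICC named for agreement has no site term; any mean site difference would lower it

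*Protocol*

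**What the plan says.** Protocol section 3.3, aim (ii), sets out to determine the variation in cerebral oxygenation "recorded using randomised (for superior/inferior) simultaneous application of the INVOS™ and FORE-SIGHT® oximeters". The Introduction (section 2) gives the reason: "the sensors will be placed randomly on the forehead in terms of superior and inferior in the same position to avoid sequential bias". The accompanying hypothesis in section 3.6 is that "The INVOS™ 5100 and the FORE-SIGHT® monitors will show no significant difference in their ability to measure cerebral oxygenation".

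Section 10.1 then names a single analysis for the device comparison: "the agreement between these pairs of observations will be assessed using intra-class correlation (ICC 3,1". The protocol does not say how sensor site enters this or any other analysis. Section 10.1 does name recorded factors to be examined as confounders ("The potential contribution of type of surgery, the length of surgery and the nature of the anaesthetic agents"), but that passage belongs mainly to the regression work on desaturation events, so the absence of sensor site from it shows little either way.

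**The concern.** Randomising which device takes the superior site balances site across devices on average. It does not balance site within a patient: on the natural reading, each patient has one device at each site. A site difference therefore shows up as a difference between devices, in one direction for about half the patients and in the other for the rest.

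ICC(3,1) discounts a constant offset between devices, but an offset that changes sign from patient to patient is not constant and is counted as error. Research question (ii) asks whether the devices vary in what they measure. If the sites differ, a low ICC could not be attributed to the devices alone.

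**Working it through.** **Plan's own figure.** There is none to reproduce. The protocol states no target ICC, precision, SD or site offset for the device comparison. Its one sample size calculation concerns the cognitive outcome and does not bear on this point.

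**Model.** Take one pair of absolute rSO2 readings per patient, one device at each site, with placement random and balanced. Let sb be the between-patient SD, se the error SD of a single reading, and d the mean superior-minus-inferior difference. Each reading is overall mean + patient + device ± d/2 + error, with + for superior and − for inferior.

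**Step 1, mean squares.**
- Patient means contain +d/2 and −d/2 once each, so site cancels: BMS = 2·sb² + se².
- The paired device difference carries +d or −d. Its variance is 2·se² + d², so EMS = se² + d²/2.

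**Step 2, coefficient.** ICC(3,1) = (BMS − EMS)/(BMS + EMS) = (sb² − d²/4)/(sb² + se² + d²/4). With d = 0 this is sb²/(sb² + se²).

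**Step 3, numbers.** Assume sb = 6 and se = 3 rSO2 points. These SDs and the offsets below are assumptions. The half-width of the 95% limits of agreement is 1.96·√(18 + d²).

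| Assumed d | ICC(3,1) without site | 95% half-width |
|---|---|---|
| 0 | 36/45 = 0.80 | 8.3 |
| 2 | 35/46 = 0.76 | 9.2 |
| 4 | 32/49 = 0.65 | 11.4 |
| 6 | 27/54 = 0.50 | 14.4 |

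**Step 4, other assumed SDs.**
- sb = 8, se = 4: 64/80 = 0.80 at d = 0, 63/81 = 0.78 at d = 2, 60/84 = 0.71 at d = 4.
- sb = 6, se = 4: 36/52 = 0.69 at d = 0, 32/56 = 0.57 at d = 4.
- sb = 8, se = 3: 64/73 = 0.88 at d = 0, 60/77 = 0.78 at d = 4.

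Across these sets, the loss at d = 2 is about 0.02 to 0.04.

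**Step 5, simulation.** This used 200 patients, balanced random placement, a true device offset of 5 points and 2,000 runs per setting. Results with sb = 8 and se = 4:
- Ignoring site, the mean ICC was 0.80, 0.78, 0.71, 0.61 and 0.50 for d = 0, 2, 4, 6 and 8, in line with the formula.
- With a site term, the ICC stayed at 0.80 throughout and the half-width at 11.0 to 11.1. Without the term, the half-width rose from 11.1 to 19.2.
- The estimated mean device difference was 5.0 points in every setting, so random placement does protect it.
- Under fixed placement the ICC also stayed at 0.80, but only because the site difference was absorbed into the device offset. Randomising is therefore the better design, provided the analysis uses it.

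**The case against.** **This is detail for the statistical analysis plan.** Section 10.1 gives one sentence on the device comparison and does not say that placement will be ignored. A plan not shown here could add the term. That stands as a reason to grade the point low. It does not remove the point, because the protocol names a particular coefficient that, in its standard form, cannot use the factor the protocol randomises.

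**The size is assumed.** This stands. Nothing in the protocol says that a superior-inferior offset exists. The fall to 0.50 needs an offset as large as the whole assumed between-patient SD. A reader might infer that the plan will make the devices look less interchangeable than they are; the protocol supports that only if there is a mean site difference.

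**The hypothesis is about a difference between monitors.** A reader might infer that the device comparison is biased. It is not: random placement keeps the mean device difference unbiased. Only the agreement statistic is affected, and the protocol ties no threshold or decision to it.

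**The device outcome may not be absolute rSO2.** The summary in section 1 lists the frequency of desaturation events by device, and section 8.2 defines an event as a relative fall of at least 20% from baseline or a value below 50%. A stable site offset largely cancels in change from the sensor's own baseline, though it would still matter for the absolute limit. The point should not be extended to event counts in general. Section 2 also describes continuous timestamped records, and the protocol does not define a pair of observations, so one pair per patient is one reading among several.

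**The placement wording is loose.** One device per site in each patient is the natural reading of sections 2 and 3.3, but the number of sensors per device and the unit of randomisation are not stated.

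**Recording.** A reader might infer that placement goes unrecorded. The data collection form is visible only in part, so that cannot be claimed.

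**Conclusion.** The point holds conditionally. If absolute rSO2 differs on average between the superior and inferior sites, ICC(3,1) computed on the device pairs without a site term understates consistency between the devices, and limits of agreement from the same pairs would be too wide. The mean device difference is unaffected.

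The size cannot be fixed from the protocol. Under the main assumed SDs the ICC drops by 0.04, 0.15 or 0.30 for offsets of 2, 4 or 6 points, and by nothing if there is no offset. The result rests on one device per site in each patient and on one pair of absolute readings per patient. This is a free improvement to the analysis of a secondary aim. It does not threaten the primary aim or the unbiasedness of the device comparison.

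**What to change.** In section 10.1, for absolute rSO2, fit device and randomised site (superior/inferior) as fixed effects with patient as a random effect. Take the ICC and any limits of agreement from that model's variance components, and report the site effect separately with its confidence interval. Make sure that the placement actually used for each patient is in the analysis dataset.

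State the limit of this adjustment: it removes only the average site effect. With one device per site, patient-specific site variation cannot be separated from device disagreement, so the adjusted agreement still contains both.

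The cost is one model term and, if placement is not already captured, one recorded field. No extra procedure or participant is needed.

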3.4 RESEARCH QUESTION

There are three research questions correlating with the three research aims;

- (i) Is cerebral desaturation during shoulder surgery associated with POCD?
- (ii) Do the FORE-SIGHT® and INVOS™ 5100 devices vary in their measurement of cerebral oxygenation during shoulder surgery in the BCP?

- (iii) Is there a relationship between cerebral desaturation events during shoulder surgery in the BCP and variables including mean arterial blood pressure, post-operative nausea/vomiting, length of hospital stay, BMI, hypertension and any adverse events?

3.5 NULL HYPOTHESES

The three null hypotheses are;

- (i) Cerebral desaturation as measured using cerebral oximetry is not related to POCD after shoulder surgery in the BCP.
- (ii) There is no significant difference between the INVOS™ 5100 and the FORE-SIGHT® monitors assessment of cerebral oxygenation during shoulder surgery in the BCP.
- (iii) There is no relationship between cerebral desaturation events during shoulder surgery in the BCP and variables including mean arterial blood pressure, the frequency of post-operative nausea/vomiting, length of hospital stay, BMI, hypertension and any adverse events.

3.6 PRIMARY HYPOTHESES

The primary research hypotheses are;

- (i) Cerebral desaturation events during surgery in the BCP will be related to POCD.
- (ii) The INVOS™ 5100 and the FORE-SIGHT® monitors will show no significant difference in their ability to measure cerebral oxygenation.
- (iii) Cerebral desaturation events experienced during shoulder surgery in the BCP are related to a drop in mean arterial blood pressure, an increased likelihood of post-operative nausea and vomiting, greater length of hospital stay, a higher BMI, hypertension and greater frequency of adverse events.

4 INVESTIGATOR RESPONSIBILITY

The investigators will be responsible for:

- Obtaining ethical clearance prior to the commencement of the study;
- Recruitment;
- Providing participants with informed consent prior to allocation of intervention;
- Provision of intervention;
- Concise and comprehensive collection of medical history, baseline demographic data, intra-operative measures and cognitive assessments;
- Ensuring confidentiality of data collection forms and results;
- Ensuring data is kept in a safe, secure and lockable location, and electronic copies have been backed up on a secure server;

- Ensuring the study is conducted in a safe and ethical manner in line with Queensland Health policies and procedures, National Health and Medical Research Council (NHMRC) guidelines and relevant laws;
- Maintaining the confidentiality of participant records and data collected, and abiding by the NHMRC guidelines for Human Research;
- Data input from paper into electronic format;
- Paper preparation and submission;
- Adherence to the Good Clinical Practice Guidelines.

A statistician will assist with the power calculation, data analysis and interpretation.

The Primary Investigators will be responsible for monitoring the implementation of the study and study processes in line with the study protocol. Any adverse events will be reported to the ethics committee.

5 STUDY DESIGN AND METHODS

5.1 GENERAL

This study aims to examine the relationship between cerebral desaturation measured via oximetry during shoulder surgery in the BCP, and POCD. Patients treated by the Principal Investigators who meet the selection criteria, will be invited to participate in this prospective study. The investigation will be conducted at the Brisbane Hand and Upper Limb Research Institute at the Brisbane Private Hospital, Brisbane, Australia.

5.2 DESIGN

A prospective cohort design will be implemented.

5.3 PARTICIPANT ELIGIBILITY CRITERIA

5.3.1 INCLUSION CRITERIA

Patients meeting the following inclusion criteria will be invited to participate in the study (see 15.1);

- Receiving treatment primarily by, but not restricted to, one of the Primary investigators for a shoulder condition that requires surgery in the BCP.
- Over 18 years of age
- Able to read and speak English

5.3.2 EXCLUSION CRITERIA

Patients will be excluded from the study for the following reasons (see 15.1);

- Under 18 years of age
- Pregnant women

- Pre- operative Mini-Mental State Examination (MMSE) < 24
- Pre-existing cerebrovascular disease as reported by the assessing medical consultant and recorded in patient charts
- Orthostatic hypotension
- ASA physical status IV and V*
- History of drug and/or alcohol abuse
- Neurological disease (e.g. previous stroke)
- Significant mood and anxiety disorders as determined by treating consultant.
- Any other condition, which in the opinion of the investigators, would render the patient unsuitable for participation in the study

* ASA = the American Society of Anaesthesiologists physical status classification system. Level IV indicates the presence of severe systemic disease that is a threat to life. Level V is a moribund person who is not expected to survive without some form of surgery.

5.3.3 WITHDRAWAL OF PARTICIPANTS DURING TRIAL

Participants may decide not to proceed with their surgery for personal reasons. We will, however, record any other type of intervention they have chosen to have at this stage (e.g. physiotherapy, injection). Those who withdraw during the follow up period will be noted and this will be reported in the final report. The sample size calculation in the study has allowed for dropouts. Dropouts will be compared to study participants according to their baseline characteristics as part of the final analysis in order to assess for differential attrition.

5.4 RECRUITMENT

The study patient population will be recruited primarily from the private consulting practices of the Principal investigators at the Brisbane Hand and Upper Limb Clinic at the Brisbane Private Hospital. All patients who are undergoing surgery in the beach chair position will be approached by a member of the research team or a research assistant employed by BHULI after they have indicated to the consultant their interest in participating in the study after the decision to undertake surgery has been made. Indeed all patients who are undergoing shoulder surgery in beach chair position by any of the surgeons involved the study would be undergoing surface cerebral oximetry anyway. There is no question that the discussion regarding participating in the study would not happen until it was already established that the patient was undergoing shoulder surgery in the beach chair position. It has nothing to do with the clinical discussion regarding the patient's treatment.

5.5 SAMPLE SIZE

Approximately 200 participants will be recruited to the study. Based on historical patient presentation rates for this group, it is anticipated that recruitment will take approximately 24 months. This allows for 75% recruitment rate and 30% loss to follow up.

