1 CLINICAL INVESTIGATION PLAN SUMMARY – PART ONE

TITLE	Prediction of post-operative cognitive decline following shoulder surgery in the beach chair position: the value of cerebral oximetry.
INVESTIGATORS	Principal: Associate [name], [name], [name], [name] Associate: [name], [name], [name], [name], [name]
OBJECTIVES	Primary aim: To examine the relationship between cerebral desaturation during shoulder surgery in the beach chair position, and post –operative cognitive decline. Secondary aims: 1. To determine the variation in cerebral oxygenation recorded using simultaneous application of the INVOS™ and FORE-SIGHT® oximeters, during shoulder surgery in the beach chair position. 2. Assess the relationship between cerebral oxygen desaturation and mean arterial pressure, incidence of nausea / vomiting, duration of hospital stay, BMI, hypertension and adverse events.
STUDY DESIGN	A prospective cohort study.
SITES	Brisbane Private Hospital.
NUMBER OF SUBJECTS	Approximately 200 participants will be recruited to this study.
TARGET POPULATION	Participants will be adults who require shoulder surgery in the beach chair position.
LENGTH OF CLINICAL INVESTIGATION	It is anticipated that this study will require 27 months from commencement of recruitment to final data collection phases (24 month recruitment period). The primary end point of the study will be 3 months post-surgery. Participants will be assessed 1 day prior to surgery (baseline), at day 1 post-surgery (early), between 10 & 14 days (mid), at 1 month (late) and at 3 months post –surgery (late).
OUTCOMES	Primary Post- operative cognitive decline will be defined as a drop of 1 standard deviation or more from baseline on 2 or more neuropsychological indices (Tournay-Jette et al., 2011). The following neuropsychological tests will be used; 
• Logical memory test• Trail making test: Delis-Kaplan Executive Function System• Single letter verbal fluency• Stroop test: Victoria’s version• List Learning: Rey Auditory Verbal Learning Test• Letter-Number Sequencing (from Wechsler Adult Intelligence Scale, 4th edition).

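### 193 with data needed, about 200 recruited and 30% loss do not fit together: if 200 is the enrolled number, about 140 remain and power is about 64–73%, not 80%

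*Protocol*

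**What the plan says.** Four places in the protocol bear on the size of the primary analysis.

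- **Section 10.1** assumes that 62% of patients do not desaturate, that 29% of these develop postoperative cognitive decline (POCD), and that desaturation raises the risk 1.75 times, which the protocol gives as 50%. With alpha 0.05 and 80% power it concludes that "we will be required to collect postoperative data on 193 participants". Later it says of the regression analyses: "With an anticipated sample size of 200 this should provide adequate numbers for our analysis".
- **Section 1**: "Approximately 200 participants will be recruited to this study". The same summary puts the primary end point at 3 months after surgery.
- **Section 5.5**: "Approximately 200 participants will be recruited to the study". It then says "it is anticipated that recruitment will take approximately 24 months", and continues: "This allows for 75% recruitment rate and 30% loss to follow up".
- **Section 5.3.3**: "The sample size calculation in the study has allowed for dropouts".

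**The concern.** The 193 in section 10.1 is a number with outcome data. Nothing in its inputs is a dropout term. The target of about 200 exceeds it by 7, yet the protocol expects up to 30% loss and says that dropouts have been allowed for. Nowhere does it say whether 200 counts people enrolled or people with data.

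The two meanings differ by 60 participants in the primary analysis (200 against 140). If 200 is the enrolled number, a null result would be judged against a claimed 80% power that the plan's own loss figure does not support. That matters here because section 2 reports that the one earlier beach-chair study of this question put its null result down to insufficient power. If 200 is the evaluable number, the enrolment needed to deliver the planned power is missing from the protocol.

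**Working it through.** **Inputs (section 10.1 unless noted).** Risk without desaturation p1 = 0.29. Risk with desaturation p2 = 0.50 as stated, or 1.75 × 0.29 = 0.5075 unrounded. Split 0.62 : 0.38. Alpha 0.05; sidedness is not stated and two-sided is assumed. Power 80%. Loss 30% (section 5.5). Recruited: about 200 (sections 1 and 5.5).

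**Step 1: reproduce 193.** Total N without continuity correction, with p̄ = 0.62 p1 + 0.38 p2:

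N = { 1.960 √[p̄(1−p̄)(1/0.62 + 1/0.38)] + 0.842 √[p1(1−p1)/0.62 + p2(1−p2)/0.38] }² / (p2 − p1)²

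For p2 = 0.50, p̄ = 0.3698 and N = (1.949 + 0.837)² / 0.21² = 176.1. The usual continuity correction raises this to 195.8 (197 if each group is rounded up, 122 + 75).

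| Required total N | p2 = 0.50 | p2 = 0.5075 |
|---|---|---|
| Two-sided, corrected | 195.8 | 183.5 |
| Two-sided, uncorrected | 176.1 | 164.5 |
| One-sided, corrected | 158.3 | 148.4 |
| One-sided, uncorrected | 138.7 | 129.6 |

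The stated 193 lies within 1.5% of the two-sided corrected figure at 50%. No other variant comes as close and none returns exactly 193. None contains a dropout allowance, so 193 is an evaluable number.

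**Step 2: the allowance actually made.** 1 − 193/200 = 3.5%.

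**Step 3: what 30% loss does.** 200 × 0.70 = 140, which is 53 short of 193. Conversely, 193/0.70 = 275.7, so 276 enrolled are needed for 193 with data, and 200/0.70 = 285.7, so 286 for 200 with data.

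**Step 4: power.** Power = Φ{ [(p2 − p1) − c − 1.960 × SE0] / SE1 }. SE0 and SE1 are the standard errors under the null and the alternative; c = ½(1/n1 + 1/n2) with the correction and 0 without.

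For N = 140 and p2 = 0.50: n1 = 86.8, n2 = 53.2, SE0 = 0.08406, SE1 = 0.08409, c = 0.01516.

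- Corrected: (0.21 − 0.01516 − 0.16475)/0.08409 = 0.358, so power is 64.0%.
- Uncorrected: (0.21 − 0.16475)/0.08409 = 0.538, so power is 70.5%.

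| Evaluable N | p2 = 0.50, corrected / uncorrected | p2 = 0.5075, corrected / uncorrected |
|---|---|---|
| 193 | 79.4% / 83.5% | 82.2% / 85.9% |
| 200 | 80.9% / 84.7% | 83.6% / 87.1% |
| 160 (20% loss) | 70.6% / 76.1% | 73.7% / 78.9% |
| 140 (30% loss) | 64.0% / 70.5% | 67.1% / 73.4% |

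Exact enumeration at 140 (87 and 53 per group) gives 67.2% for Fisher's test and 70.9% for chi-square at 50%, and 70.2% and 73.7% at 50.75%.

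**Step 5: loss that 200 enrolled could absorb at 80% power.** 1 − 195.8/200 = 2.1% corrected and 1 − 176.1/200 = 12.0% uncorrected at 50%; 8.2% and 17.7% at 50.75%. All are below 30%.

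**Step 6: risk ratio detectable with 80% power** (corrected / uncorrected): 1.73 / 1.69 with 193 evaluable, 1.87 / 1.82 with 140.

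**The case against.** The best defence is that the 30% in section 5.5 is not applied to the 200 at all. The sentence follows directly on the 24-month forecast, and a 75% recruitment rate cannot shrink a group already recruited; it makes sense only when patient presentations are turned into accrual time. The 30% stands in the same clause. On that reading 200 is the target with data, as section 10.1 suggests when it uses 200 for the analysis. Section 5.3.3 is then broadly true and power is 81–85% at 50%.

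This reading is plausible, and the power shortfall must therefore be stated as conditional. It does not rescue the text. Section 3.1 places recruitment at consent, and section 6.1 has participants booked for surgery after it, so someone recruited is not yet someone with postoperative data. The reading also needs about 286 enrolled, which no passage says and which no ordinary sense of an approximate 200 covers.

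Two further points have weight. First, 140 supposes that everyone in the 30% lacks the primary outcome. Section 10.1 names no visit for its postoperative data, and visits are tied to routine care to help retention. But section 1 sets the primary end point at 3 months, and even 20% loss leaves power below 80% on every variant. Second, the 64–73% range mixes assumptions: its upper end uses 50.75% without correction, a combination that needs about 165 rather than 193. At the stated 50% the range is 64–70% by formula and 67–71% by exact calculation.

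**Conclusion.** The concern holds. Sections 1, 5.3.3, 5.5 and 10.1 cannot all be right as worded, and at least one must change on either reading.

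- **200 enrolled (the literal wording):** about 140 are evaluable, power is about 64–70% at a 50% risk or 67–73% at 50.75%, and the statement that dropouts were allowed for is not borne out.
- **200 evaluable:** power is adequate, but sections 1 and 5.5 misdescribe the 200 and the gross enrolment of about 286 is absent.

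The figures rest on a two-sided test, the plan's own 62 : 38 split and 29% risk, and, for 140, on the full 30% lacking 3-month data. Which reading was intended cannot be settled from the protocol; that the passages conflict does not depend on it.

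**What to change.** State in sections 1, 5.5 and 10.1 whether 200 is the number enrolled or the number with primary end point data. Then:

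- **If enrolled:** give the expected evaluable number (about 140), the power this provides (about 64–70% at 50%, 67–73% at 50.75%) and the risk ratio detectable with 80% power (about 1.8–1.9), and correct the dropout sentence in section 5.3.3.
- **If evaluable:** replace the word for recruitment in sections 1 and 5.5 and state the matching gross enrolment, about 286 at 30% loss (276 would give 193 with data).

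The cost is text changes in four sections. In the first case the stated power becomes less favourable. In the second the enrolment figure rises on paper; since section 5.5 can be read as already building the 30% into the 24 months, a longer recruitment period does not necessarily follow.
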